7.5.2.3 Duration of Complete Remission

Duration of complete remission is defined as the time from start of the first documentation of complete response (CR) to the first documentation of tumor progression (PD) including radiographic evidence of progression and clinical progression per investigator or to death due to any cause, whichever comes first.

Duration of complete remission will be censored as described below:

- Patients who do not have documented tumor progression and are still on study at the time of analysis will be censored at the date of the most recent disease assessment prior to the analysis which was adequate to document progressive disease
- Patients who have started an antitumor therapy (excludes stem cell transplant or post-ASCT consolidative therapy) other than the study treatment prior to documentation of tumor progression will be censored at the date of the most recent disease assessment prior to start of new therapy which was adequate to document progressive disease
- Patients who are removed from study prior to documentation of tumor progression
 will be censored at the date of the most recent disease assessment prior to study
 discontinuation which was adequate to document progressive disease.

If a patient does not have any disease assessments adequate to detect PD after the first documentation of complete response their duration of complete remission will be censored at one day.

Duration of complete remission will only be calculated for the subgroup of patients achieving CR. Duration of complete remission will be analyzed using Kaplan-Meier methodology and Kaplan-Meier plots will be provided. The median duration of complete remission and its two-sided 95% CI using the complementary log-log transformation method (Collett, 1994) will be calculated.

7.5.2.4 Duration of Objective Response

Duration of objective response is defined as the time from start of the first documentation of objective tumor response (CR or PR) to the first documentation of tumor progression (progressive disease, PD) including radiographic evidence of progression and clinical progression per investigator or to death due to any cause, whichever comes first.

Duration of objective response will be censored as described below:

- Patients who do not have documented tumor progression and are still on study at the time of analysis will be censored at the date of the most recent disease assessment prior to the analysis which was adequate to document progressive disease
- Patients who have started an antitumor therapy (excludes stem cell transplant or post-ASCT consolidative therapy) other than the study treatment prior to documentation of tumor progression will be censored at the date of the most recent disease assessment prior to start of new therapy which was adequate to document progressive disease

• Patients who are removed from study prior to documentation of tumor progression will be censored at the date of the most recent disease assessment prior to study discontinuation which was adequate to document progressive disease.

If a patient does not have any disease assessments adequate to detect PD after the first documentation of objective response their duration of objective response will be censored at one day.

Duration of objective response will only be calculated for the subgroup of patients achieving CR or PR. Duration of objective response will be analyzed using Kaplan-Meier methodology and Kaplan-Meier plots will be provided. The median duration of objective response and its two-sided 95% CI using the complementary log-log transformation method (Collett 1994) will be calculated.

7.5.3 Additional Efficacy Endpoints

7.5.3.1 Overall Survival (OS)

Overall survival is defined as the time from date of enrollment to date of death due to any cause. In the absence of confirmation of death, overall survival time will be censored at the last date the patient is known to be alive. Patients lacking data beyond the date of enrollment will have their overall survival time censored to 1 day.

 $OS=Date\ of\ death-Date\ of\ enrollment+1.$

Kaplan-Meier Curves depicting OS will be generated. Additionally, median OS and probability of OS from 3 months to the end of the follow-up period will be reported at 3 month intervals. The two-sided 95% confidence intervals (CI) for the median and 3-month intervals will be calculated using the complementary log-log transformation method (Collett 1994).

7.5.3.2 Progression-Free Survival (PFS)

PFS is defined as the time from enrollment to the first documentation of PD or to death due to any cause, whichever comes first. Specifically, PFS will be calculated as:

PFS = Date of first documented PD or death - Date of enrollment + 1.

Progressive disease should be based on radiologic evidence of progression per investigator, but investigator claim of clinical progression will be considered adequate to document PD. In the case where both PD by radiologic assessment and clinical assessment are made, the earlier of the two possible dates is used as as the date of PD.

Censoring rules are as follows:

• Patients who do not have tumor progression and are still on study at the time of an analysis will be censored at the date of the most recent disease assessment prior to the analysis which was adequate to document progressive disease

- Patients who have started an antitumor treatment (excluding high-dose conditioning regimens pre-ASCT, consolidative radiotherapy pre- or post-ASCT, or consolidative treatment with single-agent brentuximab vedotin post-ASCT) other than the study treatment prior to documented PD will be censored at the date of the most recent disease assessment which was adequate to document PD prior to start of new therapy
- Patients who are removed from study prior to documentation of tumor progression will be censored at the date of the most recent disease assessment prior to study discontinuation which was adequate to document disease progression

If a patient does not have any adequate disease assessments after enrollment their PFS will be censored at one day.

Kaplan-Meier Curves depicting PFS will be generated. Additionally, median PFS and probability of PFS from 3 months to the end of the follow-up period will be reported at 3 month intervals. The two-sided 95% confidence intervals (CI) for the median and 3-month intervals will be calculated using the complementary log-log transformation method (Collett 1994).

An additional exploratory analysis of PFS may be conducted in which clinical assessment will be considered adequate to detect disease progression. Other exploratory analyses of PFS may also be performed. These analyses may involve different definitions of events and/or different censoring rules.

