## 6.7 Long-term Follow-up ( $\pm 2$ weeks)

Patients who discontinue from both study drugs (brentuximab vedotin and nivolumab) will remain on the study for follow-up until withdrawal of consent, death, or study closure,

whichever occurs first. Long-term follow-up assessments will be performed at the following time points post-ASCT (or post-EOT for patients who do not undergo ASCT): 100 days and then 6, 9, 12, 18, 24, 30, and 36 months and then per institutional standard thereafter.

Patients who have discontinued treatment due to PD or who have initiated subsequent systemic chemotherapy will not have response assessed but will be followed for survival. Patients will be followed at this schedule until withdrawal of consent, death, or study closure, whichever occurs first. The following assessments will be performed until disease progression; patients will be followed for survival thereafter.

- Dedicated CT of chest, neck, abdomen, and pelvis; performed at 100 days and then 6, 12, 24, and 36 months post-ASCT or post-EOT long-term follow-up visits or if progression is suspected based on clinical signs and symptoms
- PET; performed with CT scans until the patient achieves a complete metabolic response (CmR) by PET
- Interval medical history to assess changes in health status since prior visit
- Physical examination
- Disease progression status and post-study treatment received

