7.5.2.2 Progression-Free Survival (PFS) after ASCT

PFS after ASCT is defined as the time from ASCT to the first documentation of PD or to death due to any cause, whichever comes first. Patients who do not undergo ASCT or receive additional anti-cancer therapy (such as an alternate salvage regimen) prior to ASCT will not be included in the analysis of this endpoint. Date of ASCT is defined as the reported date of stem cell infusion for ASCT. Documentation of PD should be consistent with the criteria described in section 6.4. Specifically, PFS after ASCT will be calculated as:

PFS after ASCT = Date of first documented PD or death – Date of ASCT + 1.

PFS data will be censored as follows:

- Patients who do not have tumor progression and are still on study at the time of an analysis will be censored at the date of the most recent disease assessment prior to the analysis which was adequate to document progressive disease
- Patients who have started an antitumor treatment (excluding high-dose conditioning regimens pre-ASCT, consolidative radiotherapy pre- or post-ASCT, or consolidative treatment with single-agent brentuximab vedotin post-ASCT) other than the study treatment prior to documented PD will be censored at the date of the most recent disease assessment which was adequate to document PD prior to start of new therapy
- Patients who are removed from study prior to documentation of tumor progression
 will be censored at the date of the most recent disease assessment prior to study
 discontinuation which was adequate to document disease progression

If a patient does not have any adequate disease assessments after ASCT their PFS will be censored at one day.

Kaplan-Meier Curves depicting PFS will be generated. Additionally, median PFS and probability of PFS from 3 months to the end of the follow-up period will be reported at 3 month intervals. The two-sided 95% confidence intervals (CI) for the median and 3-month intervals will be calculated using the complementary log-log transformation method (Collett 1994).

Exploratory subgroup analyses may be carried out; these analyses may involve different definitions of events and/or different censoring rules.

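### Starting another salvage regimen without PD is censored in PFS and response duration, and no committed time-to-event analysis counts the switch itself as a failure

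*SAP*

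**What the plan says.** **PFS (SAP 7.5.3.2).** The event is narrow: "PFS is defined as the time from enrollment to the first documentation of PD or to death due to any cause, whichever comes first". An investigator's claim of clinical progression is enough for PD. Patients who start antitumor therapy "other than the study treatment prior to documented PD will be censored at the date of the most recent disease assessment" adequate to document PD. Conditioning before ASCT, consolidative radiotherapy and single-agent brentuximab vedotin after ASCT are exempt; another salvage regimen is not.

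**Duration of CR (SAP 7.5.2.3) and of OR (SAP 7.5.2.4).** Both have the same structure. For CR, patients who start therapy "other than the study treatment prior to documentation of tumor progression will be censored at the date of the most recent disease assessment" adequate to show PD; for OR, those who start therapy "other than the study treatment prior to documentation of tumor progression will be censored" in the same way. The OR analysis is limited to responders: "Duration of objective response will only be calculated for the subgroup of patients achieving CR or PR".

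**PFS after ASCT (SAP 7.5.2.2).** Patients who have no ASCT, or who "receive additional anti-cancer therapy (such as an alternate salvage regimen) prior to ASCT will not be included", are left out. Protocol 9.2.2.2 excludes only the first of these groups.

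**Other analyses.** OS (SAP 7.5.3.1) counts death from any cause and does not censor at new therapy. SAP 7.5.3.2 allows further exploratory PFS analyses but names only one, which would accept clinical progression. The main definition already does that. Protocol 9.2.2.3 and 9.2.3.2 said that details of alternative event and censoring definitions would appear in the SAP; none do.

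**The concern.** The regimen is meant as salvage on the way to ASCT. A patient who finishes treatment with residual disease and moves to a different salvage regimen, with no PD declared, has not had the result the regimen was meant to give. Under the rules above, that patient leaves the PFS risk set at the last adequate scan. Protocol 6.4 requires the EOT evaluations before new therapy, so this will normally be the EOT scan.

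Kaplan-Meier treats a censored patient as having the same later risk as those still followed. Protocol 1.4 gives reason to doubt that here: it cites long-term relapse-free survival after ASCT of about 75% with metabolic CR beforehand and about 25% with residual disease. Protocol 6.7 adds that response is no longer assessed once subsequent systemic chemotherapy starts, so later PD in these patients would not be collected systematically.

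At stake is how the PFS and response-duration curves read. If switching is common, they describe mainly the patients who did not need other salvage, and the PFS curve cannot show how many did.

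**Working it through.** **The plan's own figure.** No time-to-event endpoint has a stated rate, event count or power. The only powered figure is for CR rate (SAP 6.2): N = 53, reject at 22 or more CRs, null 30%, alternative 50%. The exact binomial gives type I error 0.0495 and power 0.9155, which agrees with the stated 90% or so. It does not depend on the censoring rules.

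**Where a switch without PD appears, by analysis.**
- PFS: censored.
- Duration of OR: censored if CR or PR was reached; a patient with SD is not in the analysis.
- Duration of CR: censored if CR was reached; otherwise not in the analysis.
- PFS after ASCT: excluded under the SAP.
- OS: retained; only a later death counts.
- CR rate (SAP 7.5.1.1): non-CR, if CR was never reached before the switch.
- Disposition (SAP 7.1): included in the summary of subsequent treatment.

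**A further effect on response duration.** SAP 6.4 requires CT and PET for an adequate response assessment, and the Cycle 2 scan is CT only. First response is therefore normally documented at EOT. A PR patient who then starts other salvage with no further adequate scan is censored at one day.

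**Bias in PFS (illustration).** Let f be the share censored at EOT because of a switch and p their 12-month PFS had they been followed. Assume 85% in the rest, and no events before EOT.
- True 12-month PFS = (1 − f) × 0.85 + f × p
- Kaplan-Meier with these patients censored ≈ 0.85
- Bias = f × (0.85 − p)

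With p = 0.50, the bias is f × 0.35:

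| f | Bias (points) |
|---|---|
| 10% | 3.5 |
| 20% | 7.0 |
| 30% | 10.5 |
| 40% | 14.0 |

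The interim data in Protocol 3.2.1 give a rough scale for f: 3/29 (10%) had no objective response and 11/29 (38%) had no CR. If p equals 85%, the bias is zero.

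**Bias with the protocol's own rates as assumptions.** Take 75% and 25% from Protocol 1.4, and 18 CR and 11 non-CR from Protocol 3.2.1.
- All followed: (18 × 0.75 + 11 × 0.25) / 29 = 16.25 / 29 = 56%
- Half of the non-CR patients censored at EOT: (18 × 0.75 + 5.5 × 0.25) / 23.5 = 14.875 / 23.5 = 63%
- All non-CR patients censored at EOT: 75%

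The bias is about 7 and 19 points. The 75% and 25% are post-transplant relapse-free rates, borrowed here for scale only.

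**A different quantity: PFS against event-free survival.** Assume N = 55, 3 PDs at Cycle 2, k switches without PD at about EOT, and 10% later events in the rest. The SAP rule gives 52/55 × 0.90 = 85.1% for every k. Counting switches as events gives (52 − k)/55 × 0.90: 80.2% for k = 3, 75.3% for k = 6, 67.1% for k = 11 and 50.7% for k = 21 (21 ≈ 11/29 × 55). This shows that the reported PFS does not respond to the number of switches. The gap is a difference between two endpoints, not a measure of bias.

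**The case against.** Censoring at new therapy is a legitimate PFS definition, and the failure is not hidden. A patient switched for lack of CR is a non-responder in the only tested endpoint, subsequent treatment is summarised, and OS keeps the patient. Investigator-claimed clinical progression already counts as PD, which narrows the group. The protocol makes patients eligible for ASCT after EOT without requiring CR, so a PR patient may go straight to transplant, and conditioning is exempt from censoring. PFS from enrollment is an additional endpoint with no test attached. PFS after ASCT starts at transplant and could never measure failure to reach it. All of this stands. It limits the importance of the point, but supplies no time-to-event analysis that counts the switch.

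A reader might infer more, in three ways that the documents do not support:
- That the switch is this regimen's typical failure. Nothing in either document says how often it is expected.
- That these patients disappear from every time-to-event analysis. OS retains them and counts their deaths.
- That PFS is overstated by 8.5 to 34 points for f = 10% to 40%. That is f × 0.85, the gap between event-free survival and PFS. It equals bias only if p = 0, meaning that every switched patient progresses or dies by 12 months.

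**Conclusion.** The point holds in limited form. No committed time-to-event analysis treats the start of non-exempt antitumor therapy without PD as a failure. When the switch is made for residual disease, the censoring is likely informative and PFS is likely biased upward. A switch for another reason, such as toxicity while in CR, need not bias it.

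The size cannot be derived from the documents, which give neither f nor p. Under the stated assumptions it is 3.5 to 14 points at p = 50%, and about 7 to 19 points with the borrowed 75% and 25% rates. The upper end assumes that every patient without CR is censored at EOT without PD. The primary CR test and the sample size are unaffected. This is a change that should be made for honest reading of the descriptive curves; it is not a flaw in the trial's main conclusion.

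**What to change.** Keep the main definitions.
- In SAP 7.5.3.2, commit to one named sensitivity analysis in which the start of non-exempt antitumor therapy without PD is an event on its start date (event-free survival), shown beside PFS.
- Do the same for response duration in SAP 7.5.2.3 and 7.5.2.4.
- For each endpoint, report the number of patients censored for each reason.

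Fix this before database lock, so that the choice cannot depend on the results.

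The cost is a few extra Kaplan-Meier outputs and a less favourable companion curve. No new data are needed: Protocol 6.7 already collects "Disease progression status and post-study treatment received", and the existing censoring rule cannot be applied without the start date of new therapy.

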7.5.4 Pharmacokinetic and ATA Analyses

Pharmacokinetic parameters to be estimated for brentuximab vedotin and MMAE include maximum concentration (Cmax) or concentration at the end of infusion (Ceoi), the time Cmax occurred (Tmax), and trough concentration for brentuximab vedotin (Ctrough). For nivolumab, Ceoi and Ctrough will be summarized. The incidence of ATA to brentuximab vedotin and to nivolumab will also be assessed.

If additional pharmacokinetic parameters can be estimated for some subjects, they may also be reported.

7.5.5 Biomarker Analysis

Relationships of biomarkers (e.g., baseline values, absolute and relative changes from baseline) to efficacy, safety and PK parameters will be explored. Relationships and associated data that are determined to be of interest will be summarized.

Summaries will be presented for baseline biomarker levels assessed on peripheral blood and tissue blocks or unstained slides obtained at screening to evaluate potential sensitivity or resistance to brentuximab vedotin and/or nivolumab (e.g., CD30 expression, PD-L1/L2 amplification and expression). For biomarker analyses on optional tumor biopsies obtained after disease progression or on residual disease at EOT, samples are to be tested for the expression of CD30 and PD-L1/L2 expression and other potential markers to understand potential resistance mechanisms.

The analyses for pharmacodynamic biomarkers and for biomarkers related to drug mechanism(s) of action will be defined in a separate Biomarker Analysis Plan and may be included in a separate report.

7.6 Safety Analyses

The All Treated Patients analysis set will be used to summarize all safety endpoints.

Adverse events will be coded using Medical Dictionary for Regulatory Activities (MedDRA, Version 18.0 or higher).

Laboratory values will be graded according to the National Cancer Institute (NCI) Common Terminology Criteria for Adverse Events (CTCAE version 4.03 or higher).

Concomitant medications will be coded using WHO Drug (version: June 2012 or more recent).

7.6.1 Adverse Events

Adverse events (AEs) will be listed and summarized by MedDRA preferred term, severity, and relationship to study drug in descending frequency unless otherwise specified. The incidence of all AEs, treatment-emergent AEs, and treatment-related AEs will be tabulated. For incidence reporting, if a patient reports more than one AE that was coded to the same system organ class or preferred term, the patient will be counted only once for that specific system organ class or preferred term.

A treatment-emergent AE is defined as a newly occurring or worsening AE after the first dose of brentuximab vedotin or nivolumab. The incidence of AEs will be tabulated by preferred term and presented by dose regimen and overall. Summaries will also be presented for AEs occurring prior to start of ASCT and on or after start of ASCT, where start of ASCT is defined as the start date of conditioning regimen for ASCT. Summaries of AEs will also be provided dose regimen and overall for the following:

- Pre-existing Adverse Events
- All treatment-emergent AEs
- AEs related to brentuximab vedotin
- AEs related to nivolumab
- Serious Adverse Events (SAEs)
- SAEs related to brentuximab vedotin
- SAEs related to nivolumab
- AEs leading to dose delay of brentuximab vedotin or/and nivolumab
- AEs leading to dose reduction of brentuximab vedotin or/and nivolumab
- AEs leading to dose interruption (full dose received) of brentuximab vedotin or/and nivolumab

- AEs leading to dose elimination of brentuximab vedotin or/and nivolumab
- AEs leading to treatment discontinuation
- AEs that started during infusion,
- AEs that started within 24 hours post infusion,
- Treatment-emergent AEs by system organ class, preferred term and maximum severity; at each system organ class or preferred term, multiple occurrences of events within a patient are counted only once at the highest severity
- Grade 3 5 treatment-emergent AEs
- Treatment-emergent AEs by system organ class and preferred term
- AEs of peripheral neuropathy identified by the broad search MedDRA SMQ "peripheral neuropathy"
- Infusion related reactions due to brentuximab vedotin, or/and nivolumab
- Onset of infusion reactions related to brentuximab vedotin, or/and nivolumab by preferred term by cycle

Listings will be presented for all adverse events, serious adverse events, adverse events leading to treatment discontinuation, and adverse events leading to death.

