### **3.2.1 Rationale for Study Design of Same-day Dosing**

On interim analysis, patients in Parts 1 and 2 had an ORR of 90% (95% CI 72.6%, 97.8%; 26/29 patients) and a CR rate of 62% (95% CI 42.3%, 79.3%; 18/29 patients). Similar results were reported by the ECOG-ACRIN Cancer Research Group study (E4412 Arms D and E) (ORR 100%, 8/8 evaluable patients; CR rate 62.5%, 5/8 patients), which enrolled patients with relapsed refractory HL for treatment with both brentuximab vedotin and nivolumab on Day 1 beginning with Cycle 1 ([Diefenbach 2016](#)). Based on results from both studies, a decision was made to amend the protocol to evaluate the safety and efficacy of same-day dosing of the study-drug combination beginning with Cycle 1. This new cohort, Part 3, will enroll patients with relapsed or refractory HL and will permit patients previously treated with brentuximab vedotin to explore activity of the combined regimen in brentuximab vedotin-exposed patients.

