### 7.6.1 Adverse Events

#### 7.6.1.1 Definitions

##### Adverse Event

According to the International Council for Harmonisation (ICH) E2A guideline Definitions and Standards for Expedited Reporting, and 21 CFR 312.32, Investigational New Drug (IND) Safety Reporting, an AE is any untoward medical occurrence in a patient or clinical investigational subject administered a medicinal product and which does not necessarily have a causal relationship with this treatment.

The following information should be considered when determining whether or not to record a test result, medical condition, or other incident on the Adverse Events and Pre-existing Conditions CRF:

- From the time of informed consent through the day prior to study Day 1, only study protocol-related AEs should be recorded. A protocol-related AE is defined as an untoward medical event occurring as a result of a protocol mandated procedure.
- All medical conditions present or ongoing predose on study Day 1 should be recorded.
- All AEs (regardless of relationship to study drug) should be recorded from study Day 1 (predose) through the end of the safety reporting period (see Section 7.6.1.3). Complications that occur in association with any procedure (e.g., biopsy) should be recorded as AEs whether or not the procedure was protocol mandated.
- Changes in medical conditions and AEs, including changes in severity, frequency, or character, during the safety reporting period should be recorded.
- In general, an abnormal laboratory value should not be recorded as an AE unless it is associated with clinical signs or symptoms, requires an intervention, results in a SAE, or results in study termination or interruption/discontinuation of study treatment. When recording an AE resulting from a laboratory abnormality, the resulting medical condition rather than the abnormality itself should be recorded (e.g., record “anemia” rather than “low hemoglobin”).

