### **7.6.1.3 Reporting Periods for Adverse Events and Serious Adverse Events**

The safety reporting period for all AEs and SAEs is from study Day 1 (predose) through the EOT visit or 30 days after the last brentuximab vedotin dose or 100 days after the last nivolumab dose, whichever is later. However, all study protocol-related AEs are to be recorded from the time of informed consent. All SAEs that occur after the safety reporting period and are considered study treatment-related in the opinion of the investigator should also be reported to the sponsor.

SAEs will be followed until significant changes return to baseline, the event stabilizes (recovering/resolving) or is no longer considered clinically significant by the investigator, or the patient dies or withdraws consent. All non-serious AEs will be followed through the safety reporting period. Certain non-serious AEs of interest may be followed until resolution, return to baseline, or study closure.

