APPENDIX B: DEFINITION OF THE TERM "TREATMENT-EMERGENT" WITH RESPECT TO AE CLASSIFICATION

The algorithm below should be used to determine whether an adverse event (AE) is classified as a treatment-emergent adverse event (TEAE). A TEAE is defined as any AE which is newly occurring or worsening in severity, where newly occurring means that the AE was not present at baseline. For ease of reading, both pre-existing conditions and AEs will be referred to as AEs for the remainder of this document. AE dates should be imputed in accordance with the algorithm detailed in Appendix A. prior to determination of TEAE classification. Details of the TEAE classification are as follows:

- 1) Determine the first/earliest dose date of any study treatment (for combination studies this includes any component of the regimen)
- 2) **Baseline AEs:** classify an AE as a baseline AE if it satisfies both of criteria 1 and 2 below:
 - 1. The onset period field is: "started before the signing of informed consent"; or "started after consent but before the first dose of any study treatment"; or, the onset period field is missing and the AE start date is prior to the first dose date of any study drug (step 1, above).
 - 2. The stop date satisfies either of i or ii below:
 - i. The stop date is the same as or a later date than the first dose date of any study treatment
 - ii. The stop date is missing with outcome equal to
 - recovering/resolving (this outcome may or may not be associated with a date),
 or
 - not recovered/not resolved, or
 - unknown.
 - Note: if the AE has no outcome or stop date provided, the CRF data should be queried

Note: If the event ended on Day 1 (the date of first dose of any study drug) it will be considered a baseline event.

- 3) **Post-baseline AEs:** classify an AE as post-baseline if it meets either of criteria 1 or 2 below:
 - 1. The onset period of the AE is "started after the first dose of any study treatment"
 - 2. The onset period of the AE is missing and the AE start date is the same as or a later date than the first dose date of any study treatment
- 4) Compare post-baseline AEs to baseline AEs using the lower level term (LLT) and determine classification. Note that classification may not be possible and the TEAE variable will be missing:
 - 1. Classify all baseline AEs as not treatment emergent (not TEAEs).

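### SAP 7.6.1 splits AEs only at the start of ASCT conditioning, so AEs arising on other antitumor therapy within the 100-day window enter the all-AE, treatment-emergent, Grade 3-5 and SAE summaries

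*SAP*

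**What the plan says.** **Definition.** SAP 7.6.1: "A treatment-emergent AE is defined as a newly occurring or worsening AE after the first dose of brentuximab vedotin or nivolumab". SAP Appendix B turns this into a comparison with baseline, in which "newly occurring means that the AE was not present at baseline". Both give a start and neither gives an end.

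**Collection.** Protocol 7.6.1.1: "All AEs (regardless of relationship to study drug) should be recorded from study Day 1 (predose) through the end of the safety reporting period". Protocol 7.6.1.3 runs that period "through the EOT visit or 30 days after the last brentuximab vedotin dose or 100 days after the last nivolumab dose, whichever is later". Starting another therapy does not close it.

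**Split.** SAP 7.6.1: "Summaries will also be presented for AEs occurring prior to start of ASCT and on or after start of ASCT". The dividing date is the day on which conditioning begins. No other AE summary is divided by what the patient received after study treatment. The SAP does not say where patients who never have ASCT belong.

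**Later therapy elsewhere in the SAP.** For PFS after ASCT (SAP 7.5.2.2), patients who "receive additional anti-cancer therapy (such as an alternate salvage regimen) prior to ASCT will not be included in the analysis". Best response (SAP 7.5.1.1 and 7.5.2.1) stops at later antitumor treatment, and PFS and the duration endpoints (SAP 7.5.2.2 to 7.5.2.4 and 7.5.3.2) are censored at it.

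**What limits the problem.** SAP 7.6.1 also plans AE and SAE tables for events related to each drug. SAP 7.6.1.2 presents laboratory results only up to the EOT visit.

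**The concern.** Consider a patient not in CR at EOT who starts another salvage regimen while AEs are still being collected. Cytopenias or infections on that regimen are new since baseline and began after first dose, so they are treatment-emergent under SAP 7.6.1 and Appendix B. If they are severe or serious, they also enter the Grade 3-5 and SAE summaries. If the patient is later transplanted, they fall before conditioning, in the period a reader would naturally take to describe the study regimen before transplant.

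The SAP already accepts that toxicity from a later treatment should be shown apart: that is the purpose of the split at conditioning. It also recognises later antitumor therapy in its efficacy rules. The AE summaries, which serve a primary endpoint, are the exception.

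Protocol 2.3 also lists a safety comparison of staggered with same-day dosing. If use of other therapy differed between Parts, that comparison would carry the difference.

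**Working it through.** **The plan's own safety figure.** SAP 6.2 gives a 94% chance of seeing at least one event with a 5% true rate in 55 patients. 1 − (1 − 0.05)^55 = 0.9405, which agrees. The figure does not bear on this point, and no sample size or power statement changes.

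**How an AE on other therapy is counted**

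1. Collected? Yes, if onset is within the window of Protocol 7.6.1.3; cause is irrelevant.
2. Treatment-emergent? Yes, if absent at baseline or worse than baseline.
3. Period? Pre-ASCT if conditioning starts later; not stated if there is no ASCT.
4. In the per-drug related tables? Only if the investigator judges it related. Protocol 7.6.1.1 allows an event to be called unrelated when something else explains it better.

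**How much of the window is open.** Inputs: 21-day cycles, four cycles, the EOT visit 30 to 37 days after last dose (Protocol 6.4), nivolumab + 100 days (Protocol 7.6.1.3). Protocol 6.4 requires EOT evaluations before new therapy starts.

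- Cycle 4 Day 1 = 1 + 3 × 21 = Day 64
- End of window = 64 + 100 = Day 164
- EOT = 64 + 30 to 64 + 37 = Days 94 to 101
- Days left = 164 − 101 = 63 to 164 − 94 = 70
- Share of collection days = 63/164 = 38% to 70/164 = 43%

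If a Part 3 patient completes EOT evaluations at 15 days, the earliest scan day, 100 − 15 = 85 days remain. All of these are days on which other therapy is possible, not days on it.

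**Size (illustration only).** The documents give no share of patients receiving other therapy. Let b be the incidence of an AE term before other therapy, s the share receiving other therapy in the window, and q the chance that it causes the term. Assuming independence:

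reported incidence = b + (1 − b) × s × q

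Assumed ranges: s from 5% to 38%, q from 30% to 60%. The upper s comes from the interim result in Protocol 3.2.1, "a CR rate of 62% (95% CI 42.3%, 79.3%; 18/29 patients"): (29 − 18)/29 = 11/29 = 38% not in CR.

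| b | s = 5%, q = 30% | s = 38%, q = 60% |
|---|---|---|
| 5% | 0.05 + 0.95 × 0.015 = 6.4% | 0.05 + 0.95 × 0.228 = 26.7% |
| 20% | 0.20 + 0.80 × 0.015 = 21.2% | 0.20 + 0.80 × 0.228 = 38.2% |

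For b = 5%, that is 55 × 0.01425 = 0.8 to 55 × 0.2166 = 11.9 extra patients of 55. With s near zero the effect vanishes. The upper end is a ceiling: 26 − 18 = 8 of the 11 patients not in CR were partial responders, and the protocol lets patients go to ASCT after EOT without requiring CR.

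**The case against.** The strongest reply is that treatment-emergent status records timing, not cause. Relatedness is named in the primary safety endpoint, and the per-drug AE and SAE tables should leave out events that investigators attribute to salvage chemotherapy. This stands against a reading that a reader might take: that the SAP counts salvage toxicity as toxicity of the study drugs. It does not. It does not rescue the overall tables, though, because the related tables rest on open-label judgement and leave the all-cause summaries unchanged.

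A reader might also infer that patients never transplanted sit wholly in the pre-ASCT period, or that pre-ASCT Grade 3-5 and SAE tables are planned. The first is the likely default, but it is not written. On the second, SAP 7.6.1 promises pre- and post-ASCT summaries in one general sentence and lists the Grade 3-5 and SAE summaries by dose regimen and overall.

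Much of the safety analysis is untouched: laboratory summaries stop at EOT, and tables on infusion timing, infusion reactions and study-drug dose changes cannot absorb salvage toxicity.

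Finally, the 100-day visit exists to look for immune-mediated events (SAP 4). A main table cut at new therapy would drop late nivolumab events selectively, in patients who go on to other treatment. That objection stands and shapes the fix.

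**Conclusion.** The point holds as a gap in the AE summaries. No summary is cut at the start of other antitumor therapy, so AEs on such therapy within the window enter the all-AE, treatment-emergent, Grade 3-5 and SAE summaries. They fall in the pre-ASCT period when transplant follows; without transplant the period is undefined. On schedule the exposure is 63 to 70 days after EOT.

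The size cannot be fixed from the documents and could be small. A reader might multiply the interim shares of non-responders (3/29 = 10%) and of patients not in CR (38%) by a Grade 3 or higher rate of 50% to 80% on salvage, and infer a rise of 0.10 × 0.5 = 5 to 0.38 × 0.8 = 30 percentage points. The documents do not support that. The 50% to 80% has no source in them, the calculation supposes no earlier Grade 3 or higher event, the upper end treats every patient not in CR as receiving other therapy in the window, and the true share could lie below the lower end.

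This is a cheap improvement to the reporting of a primary endpoint. It affects no hypothesis test.

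**What to change.** In SAP 7.6.1:

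1. Keep the all-window treatment-emergent, Grade 3-5 and SAE tables as planned and do not demote them, so that delayed immune-mediated events stay visible.
2. Replace the two-period ASCT split with three periods by AE onset: (a) before the earlier of conditioning start and the first antitumor treatment outside the protocol; (b) after conditioning start; (c) after other antitumor treatment. For patients with both, state which period applies; one workable rule is the treatment started most recently before onset.
3. Classify patients without ASCT by the same rule. Those with no other antitumor treatment stay in period (a).
4. Give treatment-emergent, Grade 3-5 and SAE summaries for period (a), by dose regimen and overall.

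The added date is already needed for the response definition and for censoring; Protocol 6.7 collects post-study treatment and SAP 7.1 summarises it. Site conduct and sample size do not change. The cost is SAP wording, some programming and one extra set of AE tables. The period (a) tables will also omit delayed study-drug events with onset after new therapy, so they should be read beside the all-window tables.
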